9. RESEARCH METHODS

9.1. Study design

The study will use retrospectively collected anonymised data from all eligible patients in the Oxford-Royal College of General Practitioners (RCGP) Research and Surveillance Centre (RSC) dataset at the date of data extraction. The cohort to be used for this study has already been specified for previous work as follows:

All adults and adolescents (aged 12+) registered with practices contributing data to RCGP RCS between January 1, 2009 and December 31, 2018, will be eligible for inclusion in the study. People who have opted out of record sharing will not be included (approximately 1.8% of the adult population) and have not been uploaded to the RCGP RCS database. Cumulative lifetime incidence of AA will be estimated using cases of incident AA occurring during the observational study period (January 1, 2009 and December 31, 2018). For all analyses, the overall results including both adults

(aged 18+) and children (aged 12-17) will be published, with stratification by sex, ethnicity, deprivation quintile, geographic region and urban/rural classification.

The assessment of any associations with baseline characteristics and the outcomes of interest (objectives 2-4) will be assessed using Cox proportional hazards models (time to event outcomes) and Poisson regression (repeated event outcomes) models. Three different adjustment sets will be used for each endpoint analysis. These include: an unadjusted model, a sex and age adjusted model, and a multivariable model with an adjustment set of: body mass index (BMI), smoking status, alcohol use, and common comorbidities: type 2 diabetes, hypertension, atrial fibrillation, angina, acute myocardial infarction, stroke, heart failure, chronic liver disease, dementia, rheumatoid arthritis, asthma, chronic obstructive pulmonary disease, chronic kidney disease, malignancy and inflammatory bowel disease.

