9.2.1. AA Definition

People diagnosed with AA will be identified using diagnosis codes specific to the condition.¹¹ People will be considered to have an AA diagnosis if they had an AA specific diagnosis code and, in the subsequent 365 days, no code for an alternative diagnosis (scarring alopecia¹², traction alopecia, congenital alopecia, androgenetic alopecia, telogen effluvium, tinea capitis, trichotillomania, or secondary syphilis of the scalp).

Incident cases will be defined as people with a first ever diagnosis code of AA during the study period. People with a diagnosis of AA prior to the study period will be excluded. To increase certainty that an AA diagnosis was incident, those diagnosed within six months of registering with a practice will be excluded.

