9.2.3. Inclusion criteria

Patients must meet all of the following inclusion criteria to be eligible for inclusion in the study:

1. The cohort for this study will consist of all adults and children (aged 12+) contributing to RCGP RCS database during the study period (between January 1, 2009 and December 31, 2018 inclusive).
2. The AA population consists of patients newly diagnosed with AA at any point during the study period.

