Time off work for illness	Outcome	Defined using primary care codes for 'sick leave' or the issuing of a Med 3 certificate indicating time off work for illness
Unemployment	Outcome	Defined using primary care codes indicating unemployment or incapacity from work (IB113 [incapacity benefit] form or ESA113 form [Employment Support Allowance, which replaced IB113 from January 2011])
Body mass index	Potential confounder	Identified from primary care records using clinical codes.

Smoking status	Potential confounder	Identified from primary care records using clinical codes.
Alcohol use	Potential confounder	Identified from primary care records using clinical codes.
Type 2 diabetes	Potential confounder	Identified from primary care records using clinical codes.
Hypertension	Potential confounder	Identified from primary care records using clinical codes.
Atrial fibrillation	Potential confounder	Identified from primary care records using clinical codes.
Angina	Potential confounder	Identified from primary care records using clinical codes.
Acute myocardial infarction	Potential confounder	Identified from primary care records using clinical codes.
Stroke	Potential confounder	Identified from primary care records using clinical codes.
Heart failure	Potential confounder	Identified from primary care records using clinical codes.
Chronic liver disease	Potential confounder	Identified from primary care records using clinical codes.
Dementia	Potential confounder	Identified from primary care records using clinical codes.
Rheumatoid arthritis	Potential confounder	Identified from primary care records using clinical codes.
Asthma	Potential confounder	Identified from primary care records using clinical codes.
Chronic obstructive pulmonary disease	Potential confounder	Identified from primary care records using clinical codes.
Chronic kidney disease	Potential confounder	Identified from primary care records using clinical codes.
Malignancy	Potential confounder	Identified from primary care records using clinical codes.
Inflammatory bowel disease	Potential confounder	Identified from primary care records using clinical codes.

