9.4. Primary Endpoints

Objective 1: An incident diagnosis of AA is the date of the first diagnosis code in the record and no alternative diagnosis that merits exclusion (any form of scarring alopecia¹², traction alopecia, congenital alopecia, androgenetic alopecia, telogen effluvium, tinea capitis, trichotillomania, or secondary syphilis of the scalp) diagnosed in the subsequent 365 days from date of AA diagnosis.

Objective 2: Mental health condition outcomes will be assessed up to two years post-AA diagnosis and will comprise new onset depressive episodes, recurrent major depression, and anxiety disorders, defined by the International Statistical Classification of Diseases and Related Health Problems 10th Revision (ICD10) classification, and identified using algorithms validated for use in UK primary care data.

Objective 3: Healthcare utilisation outcomes will comprise primary care visits, dermatology referrals, referrals for psychological therapy (including those via IAPT; Improving Access to Psychological Therapies) and psychiatric reviews in the two years post AA diagnosis.

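### Calendar year of index is in none of the adjustment sets, so time trends in recording may confound comparisons between groups of AA patients in Objectives 2-4

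*Combined protocol and SAP*

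**What the plan says.** **Accrual.** Section 9.2.3 states: "The AA population consists of patients newly diagnosed with AA at any point during the study period". Section 9.2.1 adds: "Incident cases will be defined as people with a first ever diagnosis code of AA during the study period". The study period is 1 January 2009 to 31 December 2018, so index dates can fall in any of ten calendar years.

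**Outcome window.** Section 9.4: "Mental health condition outcomes will be assessed up to two years post-AA diagnosis". Healthcare use (section 9.4) and work impact (section 9.5) also run for two years after diagnosis. The clock starts at each patient's own diagnosis.

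**Models.** Section 9.1 says: "The assessment of any associations with baseline characteristics and the outcomes of interest (objectives 2-4) will be assessed using Cox proportional hazards models" for time-to-event outcomes, with Poisson regression for repeated events. The three adjustment sets, to be used for every endpoint, are "an unadjusted model, a sex and age adjusted model, and a multivariable model with an adjustment set of: body mass index (BMI), smoking status", followed by alcohol use and 15 comorbidities. The abstract repeats them. The variables table in section 9.3 has no row for calendar year, period or index year, and no period stratification or sensitivity analysis is described.

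**Matching.** Section 9.1.2 names a matched-cohort design for these outcomes. It gives no matching variables or ratio and does not mention index date.

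**A change of source within the window.** For unemployment, section 9.3 lists the IB113 form or the "ESA113 form [Employment Support Allowance, which replaced IB113 from January 2011". Either form counts as an outcome.

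**The concern.** Follow-up is measured from diagnosis, so a patient diagnosed in 2009 and one diagnosed in 2018 are compared at the same follow-up time although their outcomes were recorded years apart. Most outcomes in Objectives 3 and 4 are process codes: visits, referrals, reviews, certificates and forms. Their measured rate depends on coding and referral practice as well as on the patient. If practice drifts over the decade, and one ethnic, deprivation or regional group has more of its new cases late in the window, part of the drift will appear as a difference between groups. None of the three models can remove it, because calendar time is in none of them.

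Section 8.1 describes a subgroup analysis within the AA population. That comparison is the exposed one. Matching comparators on index date, if it is done, would help an AA versus non-AA contrast but not a direct comparison between groups of AA patients.

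**Working it through.** **1. The plan's own figure.** The only calculated figure is in section 9.7.1: with 6007 AA cases, 80% power and 5% significance, detectable differences of 1.2 points for depression (10% background) and 1.5 points for anxiety (15%). Kelsey's formula is n = (1.96 + 0.84)² × p̄(1 − p̄)(r + 1)/(r d²), with r comparators per case. Solved for d at n = 6007:

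- r = 1: 1.59 and 1.87 points
- r = 3: 1.27 and 1.51 points
- r = 4: 1.23 and 1.45 points
- r = 5: 1.20 and 1.42 points

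The stated figures fit about 4:1, but no ratio is given, so the reproduction is conditional. The present point does not depend on it.

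**2. Text check.** The sets are (i) unadjusted, (ii) sex and age, (iii) BMI, smoking, alcohol and 15 comorbidities. Calendar time is absent from all three and from section 9.3.

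**3. What the form change can affect.** With a two-year window, a case indexed in 2009 or 2010 has some or all of its window before January 2011. A case indexed from 2011 on has none. Counting both forms bridges the replacement. It does not show that the two forms are issued or coded at equal rates.

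**4. Size of the possible bias.** Split the window into halves. Let a and b be the shares of two groups' cases in the later half, and k the later/earlier ratio of recorded outcome rates. Set the true group ratio to 1 within each half. The crude ratio is then

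RR = [(1 − b) + bk] / [(1 − a) + ak].

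The documents give none of a, b or k. All are assumed.

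| Late share, a vs b | k = 1.1 | k = 1.25 | k = 1.5 | k = 2.0 |
|---|---|---|---|---|
| 50% vs 50% | 1.00 | 1.00 | 1.00 | 1.00 |
| 45% vs 55% | 1.01 | 1.02 | 1.04 | 1.07 |
| 40% vs 60% | 1.02 | 1.05 | 1.08 | 1.14 |
| 35% vs 65% | 1.03 | 1.07 | 1.13 | 1.22 |
| 30% vs 70% | 1.04 | 1.09 | 1.17 | 1.31 |

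Example: 40% vs 60% with k = 1.5 gives (0.4 + 0.9)/(0.6 + 0.6) = 1.30/1.20 = 1.08. If a = b or k = 1, the ratio is exactly 1. Conditioning on the half returns 1.00 in every cell, by construction.

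**5. Against the precision of a group comparison.** Take two equal fifths of the cases, 6007/5 ≈ 1201 each (assumed).

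- *Outcome with 10% risk:* 80% power needs about 13.7% vs 10%, a ratio of 1.37. Every cell above is smaller. A spurious 1.08 would reach significance about 10% of the time, and the extreme 1.31 about 66%.
- *Primary care visits, assuming 10 per patient over two years:* the detectable rate ratio is exp(2.80 × √(2/(1201 × 10))) = 1.04 under Poisson variance. With fivefold overdispersion it is exp(2.80 × √(5 × 2/(1201 × 10))) = 1.08. A spurious 1.08 would then be declared a disparity about four times in five.

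**The case against.** **Neither condition is shown.** The bias needs a recording trend and a calendar imbalance between groups. The documents do not tabulate index year by ethnicity, region or deprivation, and they report no recording change for mental health or healthcare use. This stands, and it is why the point is one of possible confounding. A reader might infer that disparities found under this plan would be nothing but time trends. The documents do not support that: a real difference, a trend or a mixture is equally open.

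**The one recorded change is already bridged.** Both forms count, and unemployment is a secondary endpoint. This stands. A reader might take the form change as evidence that outcome recording changed generally. It concerns one outcome only.

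**The bias may be small.** For late shares of 48% vs 60%, k of 1.1 to 2.0 gives only 1.01 to 1.08. It takes a threefold rise, say 2% to 6%, to reach (0.40 × 2 + 0.60 × 6)/(0.52 × 2 + 0.48 × 6) = 4.40/3.92 = 1.12, and nothing in the documents supports a threefold rise. This stands for outcomes near 10% risk, less so for visit counts.

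**Matching may cover it.** If comparators share the index date and the trend is proportional in both arms, AA versus non-AA ratios within each group are largely protected. Date matching is not stated, however, and it would not protect direct comparisons among AA patients.

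**Detail is deferred.** Section 9.9 leaves methods to a separate SAP that may modify the protocol. But the protocol already names the adjustment sets for every endpoint. Objectives 2 and 3 are primary, and section 9.9 would reflect major changes to primary analyses in an amendment.

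**The aim is descriptive.** A disparity averaged over 2009-2018 is a legitimate target. It is easier to interpret beside an estimate that holds index year fixed.

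**Conclusion.** The point holds as a gap in the stated adjustment. Index year is absent from every adjustment set and from the variables table, and matching on index date is not stated, although cases accrue over ten years. Secular trends may therefore confound comparisons between sociodemographic groups of AA patients in Objectives 2-4.

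The size is unknown from the documents. It is nil if either condition is missing, and about 1.01 to 1.31 over the assumed grid of unequal shares. The upper end needs both a 30% vs 70% split and a doubling of recording. For an outcome near 10% the effect is mainly a shift in the estimate. For frequent outcomes a modest bias could be reported as a finding. The omission does not invalidate the plan, and no stated figure changes. Label: cheap improvement.

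**What to change.** Before analysis, in the SAP and with a protocol amendment if section 9.9 requires one:

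- Add calendar year of index, as categories or a spline, to the age-sex and multivariable sets for all Cox and Poisson models in Objectives 2-4. For Cox models, stratifying the baseline hazard by index year is an alternative. Leave the unadjusted model as it is, so the effect of the term can be seen.
- Add index year to the variables table in section 9.3.
- Tabulate index year by ethnicity, deprivation quintile, region, urban/rural class and sex, so that readers can judge whether any imbalance exists.
- State in section 9.1.2 whether comparators are matched on index date.

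**Cost.** The diagnosis date is already needed to define the index event, and the data are already extracted (section 9.8). Ten years as categories use 10 − 1 = 9 degrees of freedom per model, against about 6,000 cases. A spline can use fewer where events are sparse.

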9.2. Setting

The RCGP RSC cohort is drawn from a large GP practices network across England, currently covering a registered population of 2.6 million people, representing a broadly representative sample of the UK.¹⁰

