9.3. Variables

The variables to be utilised are listed below:

Variable	Role	Operational definition
Age	Baseline characteristic, subgroup variable, and potential confounder	Age will be defined as of the index date.
Sex	Baseline characteristic, subgroup variable, and potential confounder	Identified from primary care records using clinical codes.
Socioeconomic deprivation	Baseline characteristic, subgroup variable and potential confounder	Defined using the Index of Multiple Deprivation which is divided into national quintiles.
Ethnicity	Baseline characteristic, subgroup variable, and potential confounder	Identified from primary care records using clinical codes.
UK geographic region	Baseline characteristic, subgroup variable, and potential confounder	The United Kingdom will be divided into nine regions: Greater London, South East, South West, West Midlands, North West, North East, Yorkshire and the Humber, East Midlands, and East of England. Geographic region will be captured from enrollment data.
Urban/Rural classification	Baseline characteristic, subgroup variable, and potential confounder	Defined as urban or rural area which will be captured from enrollment data.
Alopecia Areata	Case definition	Identified from primary care records using clinical codes.
Depressive episodes	Outcome	Defined by the International Statistical Classification of Diseases and Related Health Problems 10th Revision (ICD10) classification, and identified using algorithms validated or use in UK primary care data.
Recurrent major depression	Outcome	Defined by the International Statistical Classification of Diseases and Related Health Problems 10th Revision (ICD10) classification, and identified using algorithms validated or use in UK primary care data.
Anxiety disorders	Outcome	Defined by the International Statistical Classification of Diseases and Related Health Problems 10th Revision (ICD10) classification, and identified using algorithms validated or use in UK primary care data.
Dermatology referrals	Outcome	Identified from primary care records using clinical codes.
Primary care visits	Outcome	Identified from primary care records using clinical codes.
Referrals for psychological therapy	Outcome	Identified from primary care records using clinical codes.
Psychiatric reviews	Outcome	Identified from primary care records using clinical codes.

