9.7. Study size

9.7.1. Sample size calculations

A sample size calculation is only applicable to the incidence of mental health conditions of anxiety and depression in people diagnosed with AA.

Assuming 80% power, a 5% level of statistical significance and a background population prevalence of 15% for anxiety and 10% for depression,¹⁶ our anticipated sample size for AA (n = 6007) would be sufficient to detect a risk difference of 1.2% in depression between those with and without AA, and 1.5% difference in anxiety between those with and without AA. Sample size calculations were performed in OpenEpi,¹⁷ results are presented using methods of Kelsey.¹⁸

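### No described model or variance estimator accounts for GP practice, so intervals for region and urban/rural differences will be too narrow if outcomes vary between practices

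*Combined protocol and SAP*

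**What the plan says.** Section 9.2 gives the sampling structure: "The RCGP RSC cohort is drawn from a large GP practices network across England". Section 9.1 makes registration with a contributing practice the route into the cohort.

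For Objectives 2 to 4, section 9.1 says associations "will be assessed using Cox proportional hazards models (time to event outcomes) and Poisson regression (repeated event outcomes) models. Three different adjustment sets" will be applied. The three sets are none; age and sex; and BMI, smoking, alcohol and a list of comorbidities. The abstract repeats this. Practice is in none of the sets and is not in the variable table in section 9.3.

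On the area variables, section 9.3 says "Geographic region will be captured from enrollment data", and urban/rural class has the same source. Section 9.2.2 assigns deprivation from the patient's postcode.

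Three other places bear on the point:
- Section 9.1.2 specifies a matched cohort but does not give the matching factors or ratio.
- Section 9.9 leaves detailed methods to a SAP, and no SAP text is in the supplied document.
- Section 9.11 does not mention variation between practices; its sensitivity analyses are for missing ethnicity.

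**The concern.** Cox and Poisson models with ordinary model-based standard errors treat patients of one practice as independent. Several outcomes here are things a practice does or records: visits, referrals, Med 3 certificates, unemployment codes. If practices differ in these, outcomes within a practice are correlated. The resulting loss of information is greatest for a covariate that does not vary within practice, because its effective sample moves from the number of patients towards the number of practices.

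Comparison across groups is the purpose of the study, and Objective 1 names geographical distribution. The risk is a regional or urban/rural difference reported with an interval that is too tight. This differs from extra variation in one person's visit count: it also affects the Cox models, and a person-level dispersion factor or robust variance does not remove it.

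**Working it through.** **1. The plan's own figure.** Section 9.7.1 states: "Assuming 80% power, a 5% level of statistical significance and a background population prevalence of 15% for anxiety and 10% for depression". It then says "our anticipated sample size for AA (n = 6007) would be sufficient to detect a risk difference of 1.2% in depression" and a "1.5% difference in anxiety between those with and without AA". The method is given as "results are presented using methods of Kelsey", which for r comparators per case is

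n = (z_α/2 + z_β)² · p̄(1 − p̄)(r + 1) / (r·d²).

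Solved for d at n = 6007, two-sided:

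| r | depression (10%) | anxiety (15%) |
|---|---|---|
| 1 | 1.59 points | 1.87 points |
| 3 | 1.27 | 1.51 |
| 4 | 1.23 | 1.45 |
| 5 | 1.20 | 1.42 |

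Of these ratios only r = 4, which the protocol does not state, gives both published figures to one decimal (unrounded 1.226 and 1.454). The formula assumes independent observations, and no design effect is mentioned. The figure concerns AA against no AA, which is not a practice-level contrast, so the design effects below should not be applied to it. It shows only that clustering was not allowed for at the planning stage.

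**2. Cases per practice.** From the protocol: 2.6 million registered people and 6,007 AA cases. Assumed: mean list sizes of 8,000 to 12,000.
- Practices: 2,600,000 / 8,000 = 325; 2,600,000 / 12,000 ≈ 217.
- AA cases per practice, m: 6007 / 325 = 18.5; 6007 / 216.7 = 27.7.

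**3. Design effect for a covariate constant within practice, AA patients only.** DEFF = 1 + (m − 1)·ICC. True standard errors are √DEFF times the reported ones. Actual coverage of a nominal 95% interval is 2Φ(1.96/√DEFF) − 1.

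| ICC (assumed) | DEFF, m = 18.5 to 27.7 | √DEFF | coverage |
|---|---|---|---|
| 0.005 | 1.09 to 1.13 | 1.04 to 1.06 | 94% to 93% |
| 0.01 | 1.17 to 1.27 | 1.08 to 1.13 | 93% to 92% |
| 0.02 | 1.35 to 1.53 | 1.16 to 1.24 | 91% to 89% |
| 0.05 | 1.87 to 2.34 | 1.37 to 1.53 | 85% to 80% |

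**4. Are these ICCs plausible for an uncommon outcome?** For a 10% outcome with log-normal practice risks of log-scale SD s, ICC = p(e^{s²} − 1)/(1 − p).
- ICC 0.005 gives s = 0.21, and the middle 95% of practices spans about a 2.3-fold range in risk.
- ICC 0.02 gives s = 0.41 and about a 5-fold range.
- ICC 0.05 gives s = 0.61 and about an 11-fold range.

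The bottom row of the table is therefore demanding for an outcome such as depression.

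**5. Null simulation of the Poisson model.** 400 runs, 300 practices, no true group effect; rejection rate at nominal 5%. All settings are assumed. Monte Carlo standard error near 5% is √(0.05 × 0.95/400) ≈ 1.1 points.

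| Outcome and between-practice SD of log rate | Covariate | naive | person-robust | practice-clustered |
|---|---|---|---|---|
| mean 10, SD 0.2, extra patient variation | rural flag, practice level | 64% | 22.5% | 5.5% |
| same | deprivation, patient level | 51% | 8.5% | 6.25% |
| mean 0.1, SD 0.2 | rural flag | 4.5% | 4.25% | 3% |
| mean 0.1, SD 0.5 | rural flag | 11.75% | 11.25% | 4% |
| mean 0.1, SD 0.2 | deprivation | 6% | 6% | 5.25% |
| mean 0.1, SD 0.5 | deprivation | 6% | 5.25% | 4.25% |

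For a visit-like count and a practice-level flag, person-level robust errors leave a large excess that practice clustering removes. For deprivation, most of the naive error is patient-level overdispersion. For an uncommon outcome with modest practice variation there is nothing to correct.

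**The case against.** - **The detail may come in the SAP.** Section 9.9 defers methods, and section 9.1 names model families rather than variance estimators, so this is silence and not a stated assumption of independence. That is fair. But section 9.1 already fixes the models and adjustment sets, and the treatment of practice belongs beside them.
- **Matching may deal with it.** If comparators are matched within practice, habits that affect cases and comparators alike largely cancel in the AA-versus-comparator contrast. Section 9.1.2 neither states nor excludes this. It would not help the subgroup comparisons within the AA population described in section 8.1.
- **The size is assumed.** This stands. A reader might push the ICC to 0.10 and conclude that coverage falls to about 69%. The documents give no basis for that: for a 10% outcome it needs about a 23-fold spread in risk across the middle 95% of practices.
- **Deprivation is not a practice-level variable.** This stands. A reader might infer that deprivation intervals are affected as much as regional ones; section 9.2.2 and the simulation do not support that.
- **Practice habits will be mistaken for patient disparities.** A reader might infer this as certain. The documents do not say that practices differ in coding, referring or certifying. Regional differences in referral may also be part of what Objective 3 sets out to describe.

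**Conclusion.** The omission is real: nothing in the protocol allows for practice in the variance or the model for Objectives 2 to 4. Model-based intervals for region and urban/rural contrasts will be too narrow if outcomes vary between practices. Under the list sizes assumed above and an ICC of 0.005 to 0.05, the design effect is about 1.09 to 2.3 and coverage about 94% to 80%. This rests on assumed practice counts and ICCs, and on region and urban/rural class being nearly constant within a practice, which is likely but not stated.

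High-count outcomes such as visits are the most exposed. The effect on patient-level factors, including deprivation, is smaller. These figures use AA cases per practice and do not carry over to the Objective 1 population incidence estimates, where the same principle applies but the size was not computed. The change should be made, since it is standard and cheap.

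**What to change.** In section 9.1, or in the SAP with a reference from 9.1:
- For Objectives 2 to 4, including the subgroup comparisons within the AA population, specify standard errors clustered on practice, or a practice random intercept (Poisson) or shared frailty (Cox).
- For the Objective 1 region and urban/rural incidence estimates, specify practice-clustered or bootstrap-by-practice intervals.
- State the matching factors, including whether practice is one.
- Report between-practice variance for visits, referrals and Med 3 issue beside the group differences, as context.
- State that these steps correct the intervals and do not separate practice habits from patient disparities, so area differences carry that caveat.

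The cost is a few lines of text and a pseudonymised practice identifier. Section 9.8 says the study reuses an existing anonymised extract, and practice is not in the section 9.3 list, so confirm first that the extract holds one. The price in the results is wider intervals for area-level comparisons.
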